11.3. Procedures

11.3.1. All Adverse Events

All AEs and special reporting situations, whether serious or non-serious, will be reported from the time a signed and dated ICF is obtained until 30 days after the last dose of study drug, unless the subject withdraws consent for study participation, or starts subsequent anticancer therapy. For subjects who have received additional treatment with therapeutic intent for NKTCL during the AE reporting period, only AEs that are considered to be possibly, probably, or definitely related to study drug must be reported (unless the subject has been withdrawn from the study). Serious adverse events (SAEs), including those spontaneously reported to the investigator within 30 days after the last dose of study drug, must be reported using the SAE Form. The sponsor will evaluate any safety information that is spontaneously reported by an investigator beyond the time frame specified in the protocol.

All AEs, regardless of seriousness, severity, or presumed relationship to study drug, must be recorded using medical terminology in the source document and the eCRF. Whenever possible, diagnoses should be given when signs and symptoms are due to a common etiology (eg, cough, runny nose, sneezing, sore throat, and head congestion should be reported as "upper respiratory infection"). Investigators must record in the eCRF their opinion concerning the relationship of the AE to study therapy. All measures required for AE management must be recorded in the source document and reported according to sponsor instructions.

The sponsor assumes responsibility for appropriate reporting of AEs to the regulatory authorities. The sponsor will also report to the investigator (and the head of the investigational institute where required) all suspected unexpected serious adverse reactions (SUSARs).

For all studies with an outpatient phase, including open-label studies, the subject must be provided with a "wallet (study) card" and instructed to carry this card with them for the duration of the study indicating the following:

- Study number
- Statement, in the local language(s), that the subject is participating in a clinical study
- Investigator's name and 24-hour contact telephone number
- Local sponsor's name and 24-hour contact telephone number (for medical staff only)
- Site number
- Subject number
- Any other information that is required to do an emergency breaking of the blind.

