2.7.1. Missing/Partial Adverse Event Onset Date

If the onset date of an adverse event is missing partially, the following imputation rules will be used.

- When month and year are present and the day is missing,
 - If the onset month and year are the same as the month and year of first study treatment, the day of first study treatment or the day-component of the AE end date (possibly imputed) is imputed, whichever is earlier
 - If the onset month and year are not the same as the month and year of first study treatment, then the first day of the month is imputed
- When only a year is present or no components of the onset date are present,
 - If the onset year is the same as the year of first study treatment. If AE end date is available and is prior to first study treatment, the day and month of AE end date are imputed. Otherwise, the day and month of first study treatment are imputed
 - If the onset year is different from the year of first study treatment, the 1st of January is imputed
- If the onset date is completely missing, the date of first study treatment is imputed as the onset date.

No imputation will be done for partial or missing AE onset time.

If AE onset date needs imputation, but the AE onset time is available, the AE onset time will be dropped in the imputed AE onset date/time variable.

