6.1. Adverse Events

The verbatim terms used in the CRF by investigators to identify adverse events will be coded using the most current version of the Medical Dictionary for Regulatory Activities (MedDRA). Toxicities will be graded for severity according to CTCAE, Version 4.03. All reported adverse events with onset during the treatment period (ie, treatment-emergent adverse events, and adverse events that have worsened since baseline, and within 30 days from the last dose) will be included in the analysis and reported using descriptive statistics and frequency tabulations.

The incidence of TEAEs will be summarized overall, by MedDRA system organ class (SOC) and preferred term, by toxicity grade, and by relationship to study treatment administration.

Specifically, the following will be summarized or listed:

- All adverse events
- Grade 3 or higher adverse events
- Serious adverse events
- Adverse events leading to discontinuation of treatment
- Treatment-emergent infusion related reactions
- Adverse events leading to treatment cycle delays or dose modifications
- Adverse events leading to death

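### SAP 2.7.1 dates an AE with a blank onset to first dose even when its recorded end date is earlier, so it is counted as treatment-emergent (minor)

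*SAP*

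**What the plan says.** SAP 2.7.1 has three tiers for an incomplete AE onset date.

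- **Day missing, month and year of first dose:** "the day of first study treatment or the day-component of the AE end date (possibly imputed) is imputed, whichever is earlier".
- **Second bullet:** it opens "When only a year is present or no components of the onset date are present". Both of its branches turn on the onset year. The first begins "If the onset year is the same as the year of first study treatment", and within it comes the end-date check: "If AE end date is available and is prior to first study treatment, the day and month of AE end date are imputed". The other branch, for a different onset year, imputes 1 January.
- **Last bullet:** "If the onset date is completely missing, the date of first study treatment is imputed as the onset date".

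The section adds "No imputation will be done for partial or missing AE onset time".

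Three other passages bear on the result. Protocol 11.3.1 states that AEs "will be reported from the time a signed and dated ICF is obtained until 30 days after the last dose of study drug". Protocol 3.1 allows a screening phase of up to 21 days before Cycle 1 Day 1, and Protocol 8.1.3 starts the Treatment Phase at the first intake of study drug. SAP 6.1 selects events for analysis as "All reported adverse events with onset during the treatment period".

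**The concern.** A blank onset date falls under two bullets at once. The second cannot be carried out, because both of its branches ask about a year that is not there. The last can be carried out, but it ignores the AE end date.

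Dating an event of unknown timing to first dose is a sensible conservative convention. It stops being one when a recorded end date shows that the event was over before any daratumumab was given. Such an event would enter the treatment-emergent summaries and, where its grade or seriousness qualifies, the Grade 3 or higher and serious-event summaries. The error runs in one direction only, and a single-arm trial has no comparator against which a reader could judge it. The overlap also means that two programmers could build different tables from the same text.

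**Working it through.** The SAP gives no figure on this point, so there is none to reproduce. The check has two parts.

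**1. Following the rules**

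The rules of SAP 2.7.1 were applied to hypothetical AEs whose known end date lies 1 to 21 days before first dose, which spans the screening window. Two illustrative first-dose dates were used, 10 January and 15 June, giving 21 × 2 = 42 cases for each kind of missingness. In the day-missing and year-only cases, the known parts of the onset date were taken to match the end date. An event counts as treatment-emergent if its imputed onset is on or after the first-dose date.

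| Onset date | Treatment-emergent | Onset after end |
|---|---|---|
| Day missing | 0/42 | 0/42 |
| Year only | 0/42 | 0/42 |
| Completely missing, last bullet as written | 42/42 | 42/42 (by 1 to 21 days) |
| Completely missing, end-date check added | 0/42 | 0/42 |

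For example, take first dose on 15 June, AE end on 5 June and onset blank. The last bullet gives an onset of 15 June, which is 10 days after the event ended. If only the year is known and it is the same year, the second bullet gives 5 June and the event stays pre-treatment.

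Nothing later in the SAP repairs this. Section 2.7.2 deals only with the AE end date. By contrast, 2.7.3 re-adjusts a medication start that falls after its end, and 2.7.5 does the same for subsequent anticancer therapy. Because onset times are not imputed, time of day cannot move the event back before dosing.

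**2. Size**

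Protocol 10.8 summarises the percentage of subjects with at least one occurrence of a given AE. One misclassified subject therefore changes one row by at most 1/N:

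- Two-stage total (Protocol 10.2), N = 32: 1/32 = 3.1 percentage points.
- Interim, about 15 subjects: 1/15 = 6.7 points.
- With the optional expansion of about 35, N = 32 + 35 = 67: 1/67 = 1.5 points.

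The change is zero if the subject already has a qualifying occurrence in that row.

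**The case against.** The case against giving this weight has several parts, and most of them stand.

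- **Intent.** The second bullet names the no-components case and contains an end-date check, so the authors may have meant the check to apply. That is plausible. However, the check is nested under an onset year, and the explicit last bullet gives the opposite result. This supports calling the fault an overlap to reconcile; it does not make the text sound.
- **Rarity.** The case needs a recorded pre-dose end date and no onset day, month or year, for an event arising within about three weeks of dosing. Source records must cover all AEs (Protocol 16.4), queries are raised in the data capture tool (16.5), monitors compare the eCRF with source (16.8), and SAEs are reported within 24 hours (11.3.2). This stands. The 42 of 42 result shows what the rule does to constructed cases and says nothing about how often they occur.
- **Visibility.** The rule can only over-count treatment-emergent events, and SAP 6 puts all observations in listings, where an onset after an end date could be noticed. This also stands.

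A reader might infer three stronger things that the documents do not support.

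- *Every such event adds 3.1 points.* It does not, because incidence counts subjects and not events; 3.1 points is a ceiling for one row.
- *The related-event table is inflated.* Investigators record relationship for each AE (Protocol 11.3.1) under definitions that include timing (11.1.2). Date imputation does not change that rating, and an event that ended before dosing is unlikely to be rated related.
- *AE durations become negative in the report.* SAP 6.1 plans no summary of AE duration.

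**Conclusion.** The point holds as a minor drafting fault. Followed literally, SAP 2.7.1 gives an AE with a recorded end date before first dose and a blank onset an imputed onset on Day 1, after its own end, and counts it as treatment-emergent. The fault is confined to the completely missing onset; the day-missing and year-only rules deal with the same situation correctly.

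The effect is at most 3.1 percentage points on one table row per affected subject at N = 32, 6.7 at the interim and about 1.5 with the expansion. It is zero where the subject has another qualifying occurrence.

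This rests on two assumptions: that the last bullet governs where the two overlap, and that an onset on the date of first dose with no time recorded counts as within the treatment period. The documents do not say how often such records arise, so no expected effect on the treatment-emergent rate can be calculated. The primary endpoint and the design are unaffected.

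**What to change.** Make two edits to SAP 2.7.1:

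1. In the lead-in of the second bullet, remove the alternative for an onset date with no components, so that the bullet covers year-only dates alone.
2. Replace the last bullet with: *If no part of the onset date is recorded and the AE end date is available and falls before first study treatment, the AE end date is used as the onset date; otherwise the date of first study treatment is used.*

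This extends a check that the section already uses for year-only dates. It costs one deleted phrase, one rewritten sentence and one programming condition, with no change to data collection.

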2.7.2. Missing/Partial Adverse Event End Date

If the end date of an adverse event is missing partially, the following imputation rules will be used.

- If month and year are present and the day of the month is missing, the last day of the month is imputed.
- If only a year is present, the 31st of December is used.
- If the imputed date is later than the date of death (if available), the date of death will be used as the imputed date instead.

No imputation will be done for partial or missing AE end time.

If AE end date needs imputation, but the AE end time is available, the AE end time will be dropped in the imputed AE end date/time variable.

2.7.3. Partial Concomitant Medication Start/End Date

In case of partially missing concomitant medication start/end dates, the following imputation rules will be applied. If the date is completely missing, no imputation will be performed.

- If only the day is missing, the 15th day of the month will be used
- If both the day and month are missing, the 30th of June will be used

If the medication was taken prior to study start, and the imputed start date is after first treatment date, further adjust the imputed start date as the day prior to first dosing date; if the medication was taken after study start, and the imputed start date is prior to first dosing date, further adjust the imputed start date as first dosing date.

After applying above adjusting method, if it results in medication start date that is after medication end date, the medication start date needs re-adjustment as follows:

If medication start date was imputed then adjust as follows:

- Impute the same month and year as medication end date if the non-imputed date parts are the same
- Impute the first day of the month as medication start day

If medication end date was imputed then re-adjust medication end date to be the same as the medication start date if the corresponding non-imputed date parts match the medication start date.

Also adjust the imputed medication end date so that it is on or after first dosing date.

2.7.4. Partial Initial Disease Diagnosis Date

For partially missing initial diagnosis dates, the following imputation rules will be applied. If the date is completely missing, no imputation will be performed.

- If only the day is missing:
 - If month and year of start of 1st line of prior therapy are the same year and month of diagnosis, and day of start of 1st line of prior therapy is available, impute day with day of start of 1st line of prior therapy;
 - Otherwise, impute day with 15.

- If both the day and month are missing:
 - If year of diagnosis is the same as year of start of 1st line of prior therapy, and month information is available for start of the 1st line of prior therapy;
 - Impute month with month of start of 1st line of prior therapy;
 - If day of start of 1st line of prior therapy is available, impute diagnosis day with day of start of 1st line of prior therapy; otherwise, impute diagnosis day with 15.
 - Otherwise, impute with June 30.

2.7.5. Partial Subsequent Anticancer Therapy Start Date

If year or month of subsequent anticancer therapy start date is missing or no components of the start date are present, no imputation will be performed.

If only the day-component is missing, the following steps apply:

- If the month and year of the start date are the same as the month and year of last dosing date, the day of last dosing date or the day-component of the stop date of subsequent anticancer therapy is imputed, whichever is earlier.
- If the start month and year are not the same as the month and year of last dosing date, the first day of the month is imputed.

If after the above imputation are applied, the imputed start date is after the non-imputed end date then re-adjust the start to be the same as the end date.

No imputation will be applied for missing or partial subsequent anticancer therapy end date.

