8.2. Efficacy Evaluations

Disease evaluations will be performed at Screening, every 8 weeks (± 7 days) for the first 6 months and thereafter, every 16 weeks (± 7 days) until PD, withdrawal of consent from study participation, or the end of study.

Radiological and PET-CT scans should be performed and collected according to instructions from the independent imaging laboratory. A BICR will be performed to review all the imaging data and clinical information per pre-defined independent central review charter.

The central reviewers will assess disease status based on the Revised Criteria for Response Assessment: LUGANO classification, provided in [Attachment 6](#).¹² Similar methodology should be used for disease assessment at screening and throughout the course of the study. The treatment discontinuation due to PD should be based upon the real time reading results conducted by the central readers. On the basis of clinical information, if PD is confirmed, then for all such subjects, as soon as PD is confirmed by local assessment, the sponsor should be informed immediately.

In order to maximally reduce potential bias between different readers, rigorous methodology will be employed and thus, ensure robustness of the primary endpoint assessment of ORR which is based on BICR. All radiological scans and collected clinical information will be sent to a sponsor appointed Clinical Research Organization (CRO) for a real time BICR. All treatment decisions will be based on such timely central review result. Subjects who are determined to have progressed according to LUGANO classification by the investigator will have scans centrally reviewed for confirmation of objective disease progression. If PD is not confirmed after central review, daratumumab treatment should be continued until centrally documented PD. This procedure may not be followed if the clinical information of subject (eg, Pathologically demonstrated PD) is sufficient enough to demonstrate PD, for such cases, PD confirmation from sponsor study physician is also required.

Definition of Measurable Disease, Assessable Disease, Target Lesion, and Non-Target Lesion

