10.3.2. Secondary Efficacy Endpoint

Complete response (CR) rate is defined as the proportion of subjects who achieve CR based on BICR and will be analyzed similarly as the primary efficacy endpoint.

Progression-free survival (PFS) is defined as the duration from the date of the first daratumumab dose to the date of progression/relapse based on BICR or death, whichever comes first. For those subjects who are still alive without progression/relapse, PFS will be censored at the last adequate tumor assessment.

Duration of response (DoR) will be duration from the date of the initial documentation of a response to the date of first documented evidence of PD based on BICR (PD; or relapse for subjects who experience CR) or death. For those subjects who are still without progression/relapse, DoR will be censored at the last adequate tumor assessment.

Time to response is defined as the duration from the date of the first dose of daratumumab to the earliest date that a response (CR/PR based on BICR) is first documented. For nonresponders, it will be censored at the date of PD/relapse or the date of the last adequate disease assessment, whichever comes first.

Overall survival (OS) is defined as the duration from the date of the first daratumumab dose to the date of death. For those subjects who are still alive without progression/relapse, OS will be censored at the last date known to be alive.

For time to event endpoints (eg, PFS, OS, time to response, DoR), Kaplan-Meier estimates will be presented. Median along with corresponding 95% CIs will be obtained from the Kaplan-Meier estimates. Analysis for time to response and DoR will be for responders only.

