2.7. Imputation of Partial Dates

Unless specified otherwise, no data imputation will be applied for missing safety and efficacy evaluations. For analysis and reporting purpose, missing or partial dates in adverse event (AE onset date; AE end date), concomitant therapies (start date; end date), prior therapy (start date; end date), initial disease diagnosis date and start date of subsequent anticancer therapy will be imputed.

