5.3.1. Definition

Complete response (CR) rate is defined as the proportion of subjects who achieve CR based on BICR and will be analyzed similarly as the primary endpoint ORR.

Progression-free survival (PFS) is defined as the duration from the date of the first daratumumab dose to the date of progression/relapse based on BICR or death, whichever comes first. For those subjects who are still alive without progression/relapse, PFS will be censored at the last adequate tumor assessment. Subjects who are progression-free and alive or have unknown status will be censored at last tumor assessment. Subjects with no post baseline disease assessment will be censored on Day 1. Subjects who started a subsequent anti-cancer therapy in the absence of progression will be censored at the last disease assessment before the start of subsequent therapy. Subjects whose diseases have not progressed and who are still alive at the end of the study or clinical cutoff will be censored at the last adequate disease assessment.

Duration of response (DoR) will be duration from the date of the initial documentation of a response to the date of first documented evidence of progressive disease based on BICR (PD; or relapse for subjects who experience CR) or death and calculated only for responders. For those subjects who are still without progression/relapse, DoR will be censored at the last adequate tumor assessment.

Time to response (TTR) is defined as the duration from the date of the first dose of daratumumab to the earliest date that a response (CR/PR based on BICR) is first documented. Descriptive analysis will be performed for responders including median, mean, standard deviation, and range.

Overall survival (OS) is defined as the duration from the date of the first daratumumab dose to the date of death. Subjects who withdraw consent from the study or are lost to follow-up will be censored at the time of withdrawal or lost to follow-up. For those subjects who are still alive at the time of analysis, OS will be censored at the last date known to be alive.

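### A subsequent-therapy start date with only the day missing can be imputed before the progression scan or before the last daratumumab dose, which can turn a PFS event into a censoring

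*SAP*

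**What the plan says.** SAP 2.7 lists the dates to be completed for analysis: the "initial disease diagnosis date and start date of subsequent anticancer therapy will be imputed". SAP 2.7.5 gives the rule when only the day is missing.

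- If the therapy's month and year "are not the same as the month and year of last dosing date, the first day of the month is imputed".
- If they match the last-dose month and year, "the day of last dosing date or the day-component of the stop date of subsequent anticancer therapy is imputed, whichever is earlier".
- There is one later check: if "the imputed start date is after the non-imputed end date then re-adjust the start to be the same as the end date". No check refers to the date of progression.

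SAP 5.3.1 uses this start date for PFS: any subject that "started a subsequent anti-cancer therapy in the absence of progression will be censored at the last disease assessment before the start of subsequent therapy". Protocol 10.3.2 has no such rule. It says only: "For those subjects who are still alive without progression/relapse, PFS will be censored at the last adequate tumor assessment". SAP 5.3.1 gives no subsequent-therapy censoring for duration of response.

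Under Protocol 8.2, disease evaluations are 8 weeks apart for the first 6 months and 16 weeks apart after that.

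**The concern.** Two faults follow from the wording.

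1. **No link to progression.** A subject who progresses on a scan and then starts new therapy later in the same month can receive an imputed start before the scan. If SAP 5.3.1 is applied by comparing dates, the therapy appears to have begun in the absence of progression. The documented event is then replaced by a censoring at the previous scan, 8 or 16 weeks earlier. If progression was at the first scan, the only earlier assessment is baseline, so the subject is in effect censored at about Day 1. The error falls on subjects who did progress, so it removes events and tends to lengthen PFS.

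2. **Day numbers compared instead of dates.** In the last-dose month, the rule sets the day of the last dose against the day-component of the stop date. If the stop date lies in a later month, its day number says nothing about the start, yet it can pull the start to before the last daratumumab dose. The check against the end date already deals with courses that stop early, so the clause adds only error.

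**Working it through.** The plan gives no figure on this point. Its one design figure, 78% power for ORR, reproduces (0.781, with one-sided alpha 0.0938), but nothing below depends on it.

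**Worked dates (SAP 2.7.5 applied literally)**

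| Last dose | PD scan | True start | Stop date | Imputed start | Before PD scan? |
|---|---|---|---|---|---|
| 30 Mar | 6 Apr | 16 Apr | none | 1 Apr | yes |
| 13 Mar | 20 Mar | 28 Mar | none | 13 Mar | yes |
| 21 Mar | 28 Mar | 9 Apr | none | 1 Apr | no |
| 20 Mar | 20 Mar | 29 Mar | none | 20 Mar | no |
| 20 Mar | 20 Mar | 29 Mar | 5 May | 5 Mar | yes, and before the last dose |

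The last row is the day-number fault. A last dose on 20 Mar with a stop date of 5 Jun also gives 5 Mar. It can spread to SAP 2.1: with no end-of-treatment visit date, the last cycle ends at the earlier of last dose plus 30 days (19 Apr) and therapy start minus 1 day (4 Mar). That is 4 Mar, before the last dose.

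**Share of partial dates affected**

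Assumptions, because the documents do not give them: only the day is missing, new therapy truly starts g days after the PD scan, and the last dose is at least 1 day before the scan. The stop-date clause is left out. Take a scan on day d of a month with L days. The imputed start precedes the scan when the switch is in the same month (d + g ≤ L) and d ≥ 2. That gives L − g − 1 days per month, or none if negative. Over two ordinary years (24 months, 730 days):

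- g = 7: (730 − 24 × 8)/730 = 538/730 = 74%
- g = 14: (730 − 24 × 15)/730 = 370/730 = 51%
- g = 21: (730 − 24 × 22)/730 = 202/730 = 28%
- g = 28: (14 × 2 + 8 × 1)/730 = 36/730 = 5% (fourteen 31-day and eight 30-day months; February gives none)
- g = 35: 0%

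The gap from last dose to scan does not change these totals as long as it is at least 1 day. It only decides which bullet causes the error: at g = 14, the first-of-month bullet accounts for 20% of partial dates with a 7-day gap and 43% with a 14-day gap.

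If the last dose is on or after the scan, and new therapy follows both, the share is 0%. With a stop date 60 days after the start, the day-number clause raises it to about 0.4%.

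**Sensitivity to the dosing gap (simulation, 30-day months)**

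| Switch after PD | Last dose 0–28 days before scan | Last dose 14 days before to 14 days after scan |
|---|---|---|
| 7–28 days | 37% | 19% |
| 1–14 days | 70% | 35% |
| 14–42 days | 13% | 7% |

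**Effect on the PFS estimate**

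Simulation of 32 subjects on the protocol scan schedule with a 9-month cut-off and an assumed true median PFS of 45 to 120 days, giving about 20 to 30 events:

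- 10% partial dates, 55% of them affected: 1.1 to 1.6 events lost. The Kaplan-Meier median moves later in about 6% to 15% of simulated trials.
- 20% partial dates, 75% affected: 3.0 to 4.4 events lost. The median moves in 19% to 38%.

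The typical median did not change in either case. The losses are simply events × share partial × share affected (29.6 × 0.10 × 0.55 = 1.6; 19.9 × 0.20 × 0.75 = 3.0). They treat every event as a progression followed by new therapy, so deaths and untreated subjects would lower them.

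**The case against.** A reader might infer that this will happen often, that the rule always picks the earliest possible day, or that reported PFS will be materially inflated. The documents do not support any of these.

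- **Frequency.** Stop-date clause aside, the error needs a subsequent therapy, a date missing only its day, scan and switch in one calendar month, and a last dose before the scan. Inclusion criterion 3.1 admits only patients judged unsuitable for other treatment modalities, so many may receive nothing further. Protocol 8.1.3 requires central confirmation and sponsor sign-off before follow-up and asks that the end-of-treatment visit come before new therapy, which makes very early switches less typical. Data queries (Protocol 16.5) may recover missing days.
- **Dosing past the scan.** Stopping for PD waits for the real-time central read, and Protocol 8.1.3 allows treatment to continue after PD seen only locally. Doses after the scan are plausible, and in the last-dose month the rule then protects the event.
- **Wording.** The earlier-of clause could be read as comparing full dates, and the AE rule in SAP 2.7.1 uses similar wording. The absence of progression could be judged from the record instead of by date order.
- **Remedy.** Moving every same-month start to after progression assumes that progression always came first.

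The first two points stand and limit the claim. The third does not remove it: the text names the day-component, and nothing in the SAP says progression overrides date order. The schedule also makes a last dose before the scan quite possible. Scans at weeks 8, 16 and 24 fall nominally on Day 1 of Cycles 3, 5 and 7; if that dose is not given, the last dose is 7, 14 and 14 days earlier. The fourth point stands and shapes the fix.

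**Conclusion.** The concern holds in a limited form. Read literally, SAP 2.7.5 and 5.3.1 together can convert a BICR-documented progression into a censoring one scan interval earlier, and the day-number comparison can give a start before the last daratumumab dose. These are wrong results from a stated rule, not missing detail.

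The mechanism is certain on a date-order reading. Its frequency is not: the shares rest on assumed gaps, and the documents give no expected rate of partial dates. PFS is a secondary endpoint analysed descriptively, ORR and its decision rule are untouched, and duration of response has no subsequent-therapy censoring as written. The change should be made because it is cheap and the error runs mainly one way; it does not threaten the trial's main conclusion.

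**What to change.** In SAP 2.7.5:

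1. Delete the day-component comparison and work with full dates.
2. Set the start to the later of the 1st of the reported month and the last daratumumab dose date, if that dose is in the month. Cap it at the stop date when that is complete.
3. Where BICR PD falls in the same month and the records (PD form or discontinuation reason) show that treatment stopped for PD, do not let the imputed start precede the PD date.

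In SAP 5.3.1, state that a PD on the same date as an imputed start counts as an event. Add a PFS sensitivity analysis that ignores subsequent therapy, matching Protocol 10.3.2.

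The cost is a few SAP lines and some programming, with no new data collection. The downside is that a subject who truly switched before PD within the same month could be counted as an event. Tying step 3 to recorded evidence limits this, and the sensitivity analysis bounds it.
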